5.2 Risks

Participation in this clinical study may expose the subject to the following potential risks associated with the device and/or the procedure:

- **General or Spinal Anesthesia**

There is a potential risk of developing side effects associated with the use of anesthesia. The risks of anesthesia depend on the type of anesthesia (spinal or general), and agents and/or gases used. The risks of anesthesia include respiratory acidosis and possible respiratory depression or failure, shortness of breath, postoperative pain, hematoma (bleeding around spinal column), spinal infection (meningitis or abscess), nausea and vomiting, dizziness, drowsiness, itching, shivering, liver toxicity, sore throat or damage to throat, teeth, or vocal cords, seizures, stroke (cerebrovascular accident) or temporary loss of normal blood flow to the brain (transient ischemic attack), arrhythmia, tachycardia, trauma to the teeth or tongue, cardiovascular events, and death.

Trained professionals with extensive experience and expertise who routinely administer general anesthesia with moderate sedation to subjects will be responsible for the induction and associated monitoring required for this study. In addition, study subjects will be monitored throughout the recovery period as well after the recovery period.

- **Intraoperative risks from the TURP or Aquablation procedure**

There is a potential risk of bladder perforation or rupture, bleeding, blood vessel damage, capsular perforation, electric shock/burn, fluid overload, embolism, urethral damage causing a false passageway, urethral stricture or adhesions, and puncture of or damage to non-urinary systems.

- **Postoperative risks from the TURP or Aquablation procedure**

After the operation, there is the potential for decrease in kidney function (renal compromise, renal failure), fatigue, fever, headache, infection, abdominal pain, pelvic or buttocks pain, other muscle pain/spasms, numbness, scrotal edema or bruising, penile bruising, trauma or edema, meatal stenosis, edema, hematoma, and swelling, pain, or irritation of the bladder, perineum, prostate, and urethra. Other risks include bladder problems or damage including but not limited to reduced bladder sensation, incontinence, residual urine, bladder distention, spasm, and bladder neck contracture or stenosis. Additional post-operative risks include rectal incontinence or stenosis, urethritis, urine flow decrease, hematuria, transfusion, nocturia, and urinary symptoms such as dysuria, increased frequency, hesitation, retention, or urgency. There may also be sexual or reproductive side effects such as erectile dysfunction, painful erection, retrograde ejaculation, infertility, decreased potency, impotence, penile disorder or numbness, decrease or loss of sexual desire, and loss of orgasm.

The following are potential risks that are associated with the tests or procedures required as part of the study conduct:

- **Blood draws**

The risks of blood draws include temporary pain and discomfort from the needle stick, and/or tenderness, redness or bruising at the site, bleeding, fainting and lightheadedness. While rare, there is a possibility of infection or a local blood clot.

- **Urodynamic testing**

Risks include temporary, mild irritation of the urethra, and infection.

- **Transrectal Ultrasound (TRUS)**

The risks of TRUS include rectal pain, soreness or bruising, edema, bleeding, perforation, and infection.

- **Cystoscopy**

The risks of cystoscopy include pain, dysuria, damage to the ureteral orifice, perforation or tearing of the urethra, bleeding, and infection.

5.3 Risk Mitigation

Risks during study participation will be minimized by the following:

- Clearly defining the subject inclusion/exclusion criteria.
- The site was chosen because of proven expertise in the field of urological surgery.
- The investigator will receive specific training and instruction in the use of the study device.
- Study subjects undergo intensive monitoring throughout the study by a multidisciplinary team.
- Pre-clinical, in vitro and in vivo testing has been performed in order to optimize the device safety and function.
- Clinical testing in previous human subjects has been performed in order to optimize the device safety and function.

6 STUDY ADMINISTRATION

6.1 Clinical Events Committee

An independent Clinical Events Committee (CEC), consisting of three physicians who are not study Investigators will be utilized for this trial. This CEC will be responsible for the review and adjudication of reported adverse events up to 12 months related to the device or the procedure that occur over the course of the study per the CEC Charter. Additionally, the CEC may adjudicate other events at the request of the Data Monitoring Committee or Sponsor. The CEC adjudicators shall classify (assign relatedness) the above described adverse events based on severity and association to the procedure or other attribution.

Device- or procedure-related events which are associated with the primary safety endpoint analysis will be as adjudicated by the CEC. In the event the CEC differs from the Investigator in classification of events, the resulting CEC adjudication will be used for final analysis and reporting. Any difference between how the CEC assigns seriousness or relatedness compared to the Investigator will be communicated to the Investigator.

During the review of events, the CEC shall be blinded to the clinical site and study subjects as much as possible. A CEC Charter will be developed prior to the start of study enrollment. The CEC Charter shall include consistent definitions for each type of event and shall outline the review process.

6.2 Data Monitoring Committee

The Data Monitoring Committee (DMC) will consist of a minimum of three (3) members and this group shall also act as the steering committee chartered with advising the sponsor on the design and execution of the study, monitoring the overall implementation of the study, including subject enrollment and protocol compliance, and reviewing final primary endpoint analysis.

Membership will include only independent members and therefore will not include a study investigator or a representative from the sponsor. The DMC meetings will consist of open and closed sessions (i.e. “open” denotes sponsor staff present; “closed” denotes without sponsor staff present).

The sponsor or designate will provide the DMC with reports related to subject enrollment, procedural outcome, follow-up visits, adverse events and any other material the DMC may deem necessary to carry out its responsibilities as established at the outset of the committee in the DMC charter. The DMC will assess if early evidence exists for dramatic benefit or harm for subjects while the clinical study is in progress. The DMC will make recommendations to the sponsor concerning continuation, modification or termination of the study through completion of the final primary endpoint analysis review.

The DMC will be blinded to both the investigative sites and investigators to minimize bias. The DMC will establish and maintain a Charter detailing specific operating procedures. The DMC will review the proposed interim analysis plan and interim analysis results.

Names and contact information for all DMC members will be on-file at the sponsor and available on request.

6.3 Data Collection/Electronic Case Report Forms (e-CRF)

Case report forms will be used to collect all subject data during the study within the EDC system and are referred to as e-CRFs. The EDC system enables rapid data acquisition and cleaning through extensive data checking and query processing. Monitor visits will be conducted in regular intervals through the study based upon site enrollment rates.

Data will be entered into a secure EDC system, which allows 21 CFR Part 11 compliance. Subjects follow up visits data will be entered directly by the site with corresponding source documents maintained at the site level.

6.4 Clinical Monitoring

The study will be monitored onsite to ensure that applicable regulations are followed up to 36 months. Remote data monitoring and review will be performed for the 48 and 60 month follow-up. Written procedures will be established by PROCEPT BioRobotics or their authorized designee to ensure the quality of the study and to ensure that each person involved in the monitoring process carries out the required duties.

Prior to subject enrollment, a study initiation visit will be completed at each investigational site to ensure the following:

- IRB approval has been obtained and documented
- The Investigators and study personnel are appropriately trained and clearly understand the study
- The Investigators and study personnel accept the obligations incurred in undertaking this clinical investigation.

Periodic monitoring visits will be made at all active study sites throughout the clinical study to assure that the Investigator obligations are fulfilled and all applicable regulations and guidelines are followed. These visits will assure that the facilities are still acceptable; the protocol and investigational plan are being followed, the EC/IRB has been notified of approved protocol changes as required, complete records are being maintained, appropriate and timely reports have been made to the Sponsor and the EC/IRB, device and device inventory are controlled and the Investigator is carrying out all agreed activities.

Typically, source-document verification of eCRFs will be done shortly after the eCRFs are completed. A study termination visit will be conducted at the completion of the clinical investigation to ensure that all subject data are properly documented and that all clinical materials are returned to PROCEPT BioRobotics.

If a clinical monitor becomes aware that an Investigator is not complying with the signed Investigator's Agreement, the Investigational Plan, the requirements of 21 CFR 812/ISO 14155 (if relevant) or other applicable regulations, or any conditions of approval imposed by the IRB/EC, PROCEPT BioRobotics will either secure compliance or discontinue shipments of the device to the Investigator and terminate the Investigator's participation in the investigation.

7 STUDY REPORT AND PUBLICATION STRATEGY

7.1 Final Study Report

A Final Study Report will be prepared by PROCEPT BioRobotics with the assistance of the independent safety reviewer, which will be reviewed, approved and signed by the Investigator, and will contain clinical comments based on the data contained in the CRFs.

7.2 Publication Strategy

The study will be registered with www.clinicaltrials.gov, as recommended by the International Committee of Medical Journal Editors.

The Principal Investigator agrees to provide copies of any and all proposed manuscripts to PROCEPT BioRobotics at least 30 days in advance of submitting such proposed manuscripts to a publisher or other third party to evaluate the proposed manuscript for the following purposes:

- a) For accuracy and consonance with the study database
- b) To ascertain whether confidential information or other proprietary information of PROCEPT BioRobotics (including trade secrets and patent protected materials) is being inappropriately utilized and/or released
- c) To provide Principal Investigators with information which may not yet be available to them
- d) To provide input from other Investigators and Co-Investigators in the study, if any, regarding the content and conclusions of the proposed manuscripts.

For the avoidance of doubt, PROCEPT BioRobotics may not require any amendments to be made to the clinical data, omissions to be made to it or amendments to the Principal Investigator's interpretation thereof. The decision as to whether to amend the manuscript to include any or all of the opinions or information provided by PROCEPT BioRobotics remains that of the Principal Investigator.

If PROCEPT BioRobotics makes a good faith determination, within such 30-day period, that the publication or presentation would be detrimental to its intellectual property interests, the Principal Investigator shall refrain from submitting such proposed manuscript to a publisher or other third party for another 365 days or such earlier time that notifies PROCEPT BioRobotics to allow time to file PROCEPT BioRobotics patent applications or take other steps to protect its intellectual property interests.

8 DEFINITIONS

Hematuria Categorized as an Adverse Event – Subjects who require any of the following:

- Extended catheterization beyond 3 days
- Repeat catheterization beyond three days post treatment
- Extended Hospitalization – per hospital standard of care (Serious Adverse Event)
- Blood transfusion (Serious Adverse Event)

Non-Reportable Events - Mild to moderate symptoms that are typically associated with the usual post-operative course including but not limited to dysuria, decreased urinary flow, gross hematuria within 7 days post treatment.

Post Treatment Catheterization Rate – The proportion of participants who are catheterized within 3 days following treatment with the AQUABEAM System.

Urinary Retention Adverse Event – Subjects who present beyond three days post treatment and are unable to void requiring catheterization to resolve their symptoms.

Urinary Incontinence – Subjects who didn't require incontinence pads prior to Aquablation treatment and require more than 1 incontinence pad per day post-treatment.

## 1 Background

WATER is a prospective double-blinded randomized controlled trial of aquablation using AQUABEAM system vs. standard transurethral resection of the prostate (TURP). See protocol TP0038 for details regarding eligibility, treatments and assessments. This document describes the

study's statistical analysis plan (SAP). In this document we use the abbreviations "A" and "T" to represent aquablation and TURP.

## 2 Electronic Data Capture

PROCEPT is using "iMedNet" (MedNet Solutions, Minnetonka, MN 55305) as the electronic data capture provider. iMedNet is a fully functional, 21 CFR 11-compliant web-based system for managing case report forms and downloading study-related data.

## 3 Data Analysis Software

Statistical analysis will be done using R,\* an open source data analysis package. Analysis of the interim plan's performance characteristics, as well as the interim calculation itself, will be performed by Berry Consultants.† Selected output from statistical analyses will be shared with the study's DMC, which is being managed by Boston Biomedical Associates.‡

## 4 Analysis Cohorts

The following analytic cohorts are defined.

### 4.1 Modified Intent-to-Treat (mITT) Cohort

The mITT population includes all randomized subjects in whom the assigned device (resection loop for T or handpiece for A) is inserted into the penile urethra. A patient found at the time of the procedure to have a condition that results in study exclusion does not contribute to the mITT cohort. The mITT population is the primary analysis population for both the primary safety and effectiveness endpoints.

### 4.2 Per-protocol (PP) Cohort

The per-protocol (PP) population is all mITT subjects who:

1. meet critical study eligibility criteria;
2. have no significant protocol deviations that could affect the validity of data; and
3. have evaluable assessment for the endpoint of interest.

A significant protocol deviation means non-adherence on the part of the subject or investigator to clinically significant protocol-specific inclusion/exclusion criteria, primary objective variable criteria or critical study requirement that could affect the scientific validity of the observed data point or lead to bias. Missing data are not imputed for analyses with the PP cohort.

### 4.3 Safety Cohort

The safety analysis population includes all randomized subjects in whom the assigned BPH surgery is initiated. This cohort is used for most safety analyses.

## 5 Study Endpoints

### 5.1 Primary Safety Endpoint

The study's primary safety endpoint is the proportion of subjects with adverse events rated as probably or definitely related to the study procedure classified as Clavien-Dindo Grade 2 or higher or any Grade 1 event resulting in persistent disability (e.g. ejaculatory disorder or erectile dysfunction) evidenced through 3 months post treatment (see protocol for details). Note that the Clavien-Dindo classification scheme is for grading postoperative complications not events that

---

\* See <https://cran.r-project.org/>

† <http://www.berryconsultants.com/>

‡ See <http://boston-biomedical.com/>

reflect lack of effective treatment. The endpoint is adjudicated by the study's clinical events committee (CEC).

The primary safety endpoint is considered successful if the proportion of A subjects with the endpoint is non-inferior to the proportion of T subjects with a non-inferiority margin of 10%. Hypotheses are:

$$H_{0,S,N}: S=S_A-S_T \geq 10\%$$

$$H_{A,S,N}: S=S_A-S_T < 10\%$$

That is, if the difference in safety proportion (S) between A and T is statistically  $<10\%$ , non-inferiority will be concluded. If non-inferiority is concluded, an additional test will be performed for statistical superiority:

$$H_{0,S,S}: S=S_A-S_T \geq 0\%$$

$$H_{A,S,S}: S=S_A-S_T < 0\%$$

That is, if the difference in safety proportion (S) between A and T is statistically  $<0\%$ , superiority will be concluded. The last subscript in each of the 4 listed hypotheses is either N for non-inferiority and S for superiority. Therefore, the four safety hypotheses are:

- Null for non-inferiority
- Alternative for non-inferiority
- Null for superiority, and
- Alternative for superiority

As detailed below, an interim predictive probability of safety non-inferiority will be calculated and the study's enrollment may be enhanced to increase the chance of demonstrating superiority under certain conditions (described below). A 2-sided 95% confidence interval for the difference in proportions will be used to test for non-inferiority. Non-inferiority will be declared if the entire 2-sided 95% CI is less than 10%. A gate-keeping strategy is used such that if the non-inferiority test is positive, a superiority test will be performed. A 2-sided  $(1-\alpha)\%$  confidence interval will be used to test for superiority. Superiority will be declared if the entire 2-sided 95% CI is less than 0%. The sample size is fixed for the non-inferiority trial, but the sample size may increase (described below). For this reason, a multiplicity adjustment is required for the superiority analysis. The `testBinomial` function from the `gsDesign` package will be used to compare proportions and calculate non-inferiority and (if relevant) superiority p-values. The `ciBinomial` from `gsDesign` will be used to calculate 95% two-sided confidence limits.

FDA has suggested that the primary safety endpoint should include events deemed "possibly" related. PROCEPT believes that including such events could lead to bias, since investigators may be more likely to report an event as "possibly" related to A since A is a less familiar procedure. Independent adjudication by a CEC would not necessarily remove this reporting bias. Events that are only "possibly" related are of interest, but not as it regards an unbiased safety estimate. Based on FDA's feedback, an additional analysis will be performed including events meeting the primary safety endpoint that are "possibly" related.

## 5.2 Primary Effectiveness Endpoint

The primary effectiveness endpoint is the IPSS change score from baseline to 6 months. IPSS is an accepted and commonly used measure for symptom severity in BPH. IPSS varies from 0 (no symptoms) to 35 (maximal symptoms).

The difference in mean change scores will be calculated as  $D=D_A-D_T$ , where  $D_x$  signifies mean improvement from baseline, expressed as a positive number.  $D$  is the difference improvement; thus if the improvement is 14 points in A and 15 points in T, the difference  $D = -1$  point. The primary hypothesis is that of non-inferiority of 6-month change scores:

$$H_{0,E,N}: D=D_A-D_T \leq \text{NIM}$$

$$H_{A,E,N}: D=D_A-D_T > \text{NIM}$$

For these hypotheses, NIM is expressed as a negative number (e.g., -5 points). If non-inferiority is concluded, an additional test will be performed for statistical superiority:

$$H_{0,E,S}: D=D_A-D_T \leq 0$$

$$H_{A,E,S}: D=D_A-D_T > 0$$

The same notation is used for the last subscript: N = non-inferiority and S = superiority. Therefore, the 4 effectiveness hypotheses are:

- Null for non-inferiority
- Alternative for non-inferiority
- Null for superiority
- Alternative for superiority

A 2-sided 95% confidence interval for the difference in means will be used to test for non-inferiority. Non-inferiority will be declared if the entire 2-sided 95% CI is greater than the NIM (where NIM is expressed as a negative number). A gate-keeping strategy is used such that if the non-inferiority test is positive, a superiority test will be performed. A 2-sided  $(1-\alpha)\%$  confidence interval will be used to test for superiority. Superiority will be declared if the entire 2-sided 95% CI is greater than 0%. The sample size is fixed for the non-inferiority trial, but the sample size may increase (described below). For this reason, a multiplicity adjustment is required for the superiority analysis. Critical values will be chosen to ensure Type I error control.

The study will be deemed a non-inferiority success if both the safety and effectiveness primary endpoint null hypotheses are rejected. Additional analyses for the primary effectiveness endpoint will be performed using general linear models that incorporate potential predictors of IPSS change scores (e.g., baseline IPSS) as covariates. Subgroup analysis is described below.

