2.16 Randomization

Subjects will be prospectively randomized into one of two treatment groups. Randomization must occur prior to surgery and only after the subject provides written informed consent, completes all baseline procedures and meets the requirements of the study inclusion and exclusion criteria. Randomization should be performed as closely as possible to the point of surgery to minimize the incidence of dropout prior to treatment.

Subjects will be randomly assigned on a two to one (2:1) basis to either the treatment group (Aquablation) or the control group (TURP). Randomization will be stratified by baseline IPSS score (<20 and ≥20) and study site. Permuted block randomization will be performed within strata. To minimize the opportunity for the sequence to be predicted, the block size will be variable and randomly chosen from small multiples of 3 (i.e. 3 or 6). The randomization schedules for all strata will be generated in advance by the contracted study statistician using a computerized random number generator. Investigational sites will not have access to the randomization schedules. Any investigator who is found to tamper with the randomization scheme will be immediately terminated from the study and his/her study site data removed from analysis; patients at such sites treated under the protocol will be followed for an additional 3 months for safety purposes only.

Administration of randomization assignments will be accomplished using a web-based electronic data system. Treatment assignment is made only after verification of proper informed consent execution and study eligibility. The study coordinator or a designee will obtain the randomization assignment per the provided randomization instructions. A copy of the randomization assignment will be maintained in the subject's file.

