4.2 Primary Effectiveness Endpoint Calculation

The primary effectiveness hypothesis is a non-inferiority comparison of the mean change in IPSS score from baseline to 6 months across groups using a non-inferiority margin of 4.7 points. This type of comparison is consistent with FDA guidance [14].

For the primary effectiveness endpoint, the null hypothesis is that the mean IPSS change score for Aquablation is inferior to that for TURP, using a non-inferiority margin of 4.7 points.

The alternative hypothesis is that the mean IPSS change score for Aquablation is non-inferior to TURP, using a non-inferiority margin of 4.7 points.

These hypothesis statements are written as follows:

$$H_0: \mu_C - \mu_T \leq -\delta$$

$$H_A: \mu_C - \mu_T > -\delta$$

where μ_T and μ_C represent the mean changes in IPSS (from baseline to 6 months) for the treatment and control groups, respectively. Negative changes from baseline represent patient improvement under this design. The pre-specified non-inferiority margin (δ) is 4.7 points. The hypothesis will be tested with one-sided overall type I error controlled at 0.025 using an O'Brien-Fleming-type spending function to account for possible early stopping with a single interim analysis when all subjects are through 3 months of follow-up.

Aquablation will be declared non-inferior to TURP if it can be established that the difference in change in IPSS score between the two groups is within the non-inferiority margin of $\delta = 4.7$ points. If non-inferiority is established, a test for superiority will be conducted. If it can be established that the mean difference is statistically greater than 0 points (i.e. $\mu_T > \mu_C$), superiority will also be claimed.

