## 5.4 Study-Specific NIM

WATER will use a study-specific non-inferiority margin based on baseline IPSS score, as detailed below.

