### 5.4.2 Change Scores in TURP Trials

In Marszalek’s group of TURP trials, the unweighted average IPSS change score at 12 months was 16 points. Because TURP has a large effect on IPSS scores, a “ceiling” effect is seen (wherein score changes reach their maximum). This results in a statistical relationship between baseline score and score change (Figure 4).

[figure not shown]

Figure 1. TURP trials reported in Marszalek.

Table 1. Trials included in Marszalek et al.

Author	Baseline IPSS	IPSS at 12 months	Improvement
Gupta	23.5	6	17.5
Kuntz	21	2.4	18.6
Montorsi	22	3.8	18.2
Westernberg	23	4	19
Wilson	24	5	19
Helke	18	5.5	12.5
Gupta	23.5	6	17.5
Nuhoglu	17.5	5	12.5
Seckiner	24	8	16
Hemmadeh	27	6	21
Shokeir	25.2	5	20.2
Van Melick	17	3.5	13.5
D'Ancona	17	3	14

De la Rosette	20	3	17
Wagrell	20.5	7.5	13
Hill	24.5	8	16.5
Kabalin	18	6.5	11.5
Martenson	22	3.5	18.5
Suvakovic	18.5	7.5	11
Non-weighted average	21.4	5.2	16.2

[figure not shown]

Figure 2. Relationship between baseline IPSS score and change score in TURP studies summarized in AUA 2003 document.

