Equation (2) directly demonstrates that the mean IPSS change score representing "slight improvement" is linearly related to the mean baseline score ( $\overline{\text{Base}}$ ). The median baseline IPSS in Barry's cohort was 16, which, based on (2), corresponds to a change score representing slight improvement of approximately 3, i.e., the value reported by Barry (and applicable, we would argue, to his trial only). In TURP trials, with mean baseline scores of 20-24 (see Figure 1), the calculated change score for slight improvement would be 4.4 points for a 20-point baseline mean and 5.8 points for a 24-point baseline mean.

We will therefore calculate a study-specific NIM for WATER using (2) and the overall (both groups) baseline mean IPSS score. With an expected baseline mean IPSS score of about 23 (the mean baseline values in PROCEPT's phase 2 studies), the study-specific NIM would be approximately 5 points. This value represents the best literature-based estimate of the change score representing slight improvement in men with BPH seeking surgical treatment.

Note that FDA's guidance document on NIMs suggests choosing a NIM value (M2) that is substantially less than that of M1 such that the new treatment preserves most of the effect size compared to the standard treatment. Clearly, an M2 of approximately 5 points preserves most of TURP's effect size (10-16 points, see Section 5.4.3).

Based on FDA's feedback of August 26, 2016, an additional calculation will be made using a fixed NIM value of 4.7 points.

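### The interval that decides effectiveness omits baseline IPSS: the test is valid, but a baseline-adjusted analysis would be more precise at almost no cost

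*SAP*

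**What the plan says.** The deciding analysis is in SAP 5.2: "A 2-sided 95% confidence interval for the difference in means will be used to test for non-inferiority". The superiority test that follows uses the same kind of interval, compared with zero. No covariate or stratification term is named. Protocol 4.2 names none either; it describes "a non-inferiority comparison of the mean change in IPSS score from baseline to 6 months across groups using a non-inferiority margin of 4.7 points".

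Baseline IPSS is prominent elsewhere:

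- Protocol 2.16: "Randomization will be stratified by baseline IPSS score" (below 20, or 20 and above) and by site.
- SAP 5.4.2, on the ceiling effect with TURP: "This results in a statistical relationship between baseline score and score change".
- SAP 5.4: "WATER will use a study-specific non-inferiority margin based on baseline IPSS score, as detailed below".

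Baseline-adjusted analyses are planned, but none decides the claim. SAP 5.2 says "Additional analyses for the primary effectiveness endpoint will be performed using general linear models that incorporate potential predictors of IPSS change scores", with baseline IPSS as the example. SAP 7, item 7, adds repeated-measures models with baseline IPSS, as additional endpoints in the per-protocol cohort that are not meant to support labeling.

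The two documents also differ on the margin. Protocol 4.2 fixes 4.7 points. SAP 5.4.4 computes the margin from the overall baseline mean and says that "an additional calculation will be made using a fixed NIM value of 4.7 points".

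**The concern.** The plan treats baseline IPSS as important enough to stratify on and to set the margin, but leaves it out of the one interval that decides the claim. If baseline predicts change, part of the variance in change scores is explainable. An interval that ignores it is wider than it needs to be. Stratified allocation then adds a second effect: the groups are better balanced on baseline than the unadjusted standard error assumes, so the test is somewhat conservative.

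At stake is the chance that a truly non-inferior device fails on the deciding interval while the supporting adjusted interval passes. The superiority test would lose precision in the same way. The safety endpoint is not affected.

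**Working it through.** **Inputs from the documents.** Protocol 4.4 gives 156 evaluable subjects, which at 2:1 is 104 Aquablation and 52 TURP; SD 6; margin 4.7; assumed effect -1.5. Protocol 4.2 describes that effect as 1.5 points less improvement with Aquablation, and I read it so. One-sided alpha is 0.025 (Protocol 4.2), equivalent to the two-sided 95% interval in SAP 5.2.

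**Reproducing the stated power.** SE = 6 × √(1/104 + 1/52) = 6 × 0.1698 = 1.019. Distance to the margin = 4.7 − 1.5 = 3.2, and 3.2/1.019 = 3.14. Normal power = Φ(3.14 − 1.96) = 88.1%; noncentral t gives 87.7%. This agrees with the protocol's claim of more than 80%.

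**The SAP margin.** From SAP 5.4.4, margin = 0.3636 × baseline mean − 2.9091. SAP Table 2 estimates a mean of 22, which gives 5.09. The text of SAP 5.4.4 says "With an expected baseline mean IPSS score of about 23", which gives 5.45. The SAP itself rounds to approximately 5.

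**Assumption.** The patient-level R-squared between baseline and change is not in the documents. I use 0.04, 0.10, 0.25 and 0.50.

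**Simple formula.** Replace SD 6 by 6 × √(1 − R²), with one degree of freedom fewer (noncentral t):

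| R² | CI half-width | Power at 4.7 | at 5.09 | at 5.45 |
|---|---|---|---|---|
| unadjusted | 2.01 | 87.7% | 93.8% | 97.1% |
| 0.04 | 1.97 | 89.0% | 94.7% | 97.6% |
| 0.10 | 1.91 | 90.8% | 95.8% | 98.2% |
| 0.25 | 1.74 | 95.0% | 98.1% | 99.4% |
| 0.50 | 1.42 | 99.3% | 99.9% | >99.9% |

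The largest gains are 99.3 − 87.7 = 11.6 points at 4.7, 99.9 − 93.8 = 6.1 at 5.09, and about 2.9 at 5.45.

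**Crediting the unadjusted test for stratified balance.** The simple formula ignores the balance that stratification gives the unadjusted comparison. A simulation allowed for it: 17 sites × 2 IPSS strata, blocks of 3 or 6, 177 randomised, 156 analysed, 8,000 runs per R². The baseline distribution was assumed (range 12 to 35, mean 22.85, SD 5.13, 27% below 20; Protocol 4.2 expects 33% below 20). Power, unadjusted to ANCOVA:

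| R² | 4.7 | 5.09 | 5.45 |
|---|---|---|---|
| 0 | 86.9 to 86.7% | 93.4 to 93.2% | 96.7 to 96.8% |
| 0.04 | 87.8 to 88.8% | 94.1 to 94.7% | 97.1 to 97.5% |
| 0.10 | 87.9 to 90.6% | 94.0 to 95.6% | 97.0 to 98.0% |
| 0.25 | 88.0 to 94.5% | 94.1 to 97.9% | 97.3 to 99.2% |
| 0.50 | 90.3 to 99.4% | 95.9 to 99.9% | 98.2 to 100.0% |

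The gains are 1.0, 2.7, 6.5 and 9.1 points at 4.7; 0.6, 1.6, 3.8 and 4.0 at 5.09; and 0.4, 1.0, 1.9 and 1.8 at 5.45. The top of the range moves with the assumed design: a second simulation with baseline SD 5 reached about 10 points at 4.7 for a correlation of 0.7 (88.9 to 99.2%).

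**Validity.** Simulated one-sided type I error of the unadjusted test at 4.7 was 0.027, 0.021, 0.020 and 0.016 for R² of 0.04 to 0.50 (Monte Carlo SE 0.0017). For ANCOVA it was 0.028, 0.024, 0.023 and 0.025. The unadjusted test is not inflated and becomes conservative as R² rises.

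**Missing data.** The simulation was repeated with 21 subjects missing at 6 months, 20 imputations and an assumed 3- to 6-month residual correlation of 0.6. Power at 4.7 went from 87.1 to 88.2%, 88.5 to 91.2%, 89.7 to 95.4% and 91.0 to 99.2%, so the gain is about the same.

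**Superiority.** For an assumed true benefit of 2 points, simple-formula power rises from about 50% to 51, 54, 62 and 79%, before any multiplicity adjustment.

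**The case against.** The strongest reply is that nothing is broken. The unadjusted test is valid, clearly specified and adequately powered, and at the SAP's margin there is little power left to gain. Models with baseline IPSS are already planned in SAP 5.2 and SAP 7, and SAP 8 adds subgroups by baseline IPSS. Protocol 3.2 marks the endpoint as already reported, so the deciding analysis may no longer be open to change. The superiority gain assumes a benefit that the plan does not expect, since it assumes Aquablation is 1.5 points worse.

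Most of this stands, and it limits the point to an efficiency improvement. What it does not answer is which interval decides: planned supporting models cannot rescue a claim that fails on the unadjusted one.

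Three stronger readings are tempting and should be resisted:

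- A reader might infer that leaving out a stratification factor makes the test invalid or the trial underpowered. The type I error and power figures show neither.
- A reader might take a patient-level correlation from SAP Table 1, where mean improvement tracks mean baseline across trials (r = 0.83). That is a relation between trial averages and does not give the within-trial R-squared.
- A reader might quote a single small gain at a margin of about 5.3. The SAP states no such margin, and any single figure hides the dependence on both the margin and the unknown R-squared.

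**Conclusion.** The concern holds as a near-free gain in precision and not as an error. For assumed R-squared of 0.04 to 0.50, adjusting for baseline IPSS adds about 1 to 9 points of non-inferiority power at the 4.7 margin when the unadjusted test is credited for stratified balance, and up to about 12 by the simple formula. At the SAP formula's margin of 5.09 to 5.45 it adds about 0.4 to 4 points with the same credit (up to about 6 by the simple formula at 5.09), where unadjusted power is already about 94 to 98%. If baseline does not predict change at all, the loss is at most about 0.3 points.

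These figures rest on 156 evaluable subjects, SD 6, a true difference of -1.5 and an R-squared that is assumed throughout. Which range applies depends on which margin decides, and the protocol and SAP do not agree on that. Nothing here implies that a reported result is wrong.

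**What to change.** State in SAP 5.2, before unblinding:

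- The primary analysis is an ANCOVA of 6-month IPSS change on treatment and continuous baseline IPSS.
- Non-inferiority is declared if the two-sided 95% CI for the adjusted difference lies wholly above the NIM, in the SAP's sign convention.
- Superiority is then tested against 0, at the level set under SAP 5.3 if enrolment is increased.
- The unadjusted difference is supportive.
- Where 6-month data are multiply imputed (Protocol 4.7), the same model is fitted in each imputed data set and the results are combined.

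Site, the other stratification factor, is also absent from the deciding test; it can stay with the poolability analyses in SAP 9.

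The cost is one degree of freedom and no new data or visits. The quantity estimated remains the difference in mean change. The interim predictive calculation (SAP 5.6) and the superiority adjustment (SAP 5.3) rely on separate documents that would have to be aligned with the ANCOVA; that work cannot be sized from what is available here.

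If results are already known, as Protocol 3.2 indicates, do not change the deciding analysis. Keep the primary result and report the baseline-adjusted difference with its 95% CI beside it.
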